9.2. Clinical Laboratory Evaluations

Laboratory assessments include clinical laboratory testing, pregnancy test, and hepatitis B virus, hepatitis A immunoglobulin M, hepatitis C antibody, and human immunodeficiency virus screen. If any of the laboratory parameters of interest show a significant shift from baseline, patients will then be scheduled for an interim visit within 2 weeks to have the laboratory measurements repeated.

Routine clinical laboratory testing will be performed by a central laboratory and will include the following:

- Haematology: haemoglobin, haematocrit, red blood cell count, white blood cell count with differential, mean corpuscular volume, mean corpuscular haemoglobin, mean corpuscular haemoglobin concentration, and absolute platelet count;
- Clinical chemistry: total protein, sodium, potassium, calcium, chloride, inorganic phosphate, albumin, fasting blood glucose, glycated haemoglobin, high-density lipoprotein and low-density lipoprotein cholesterol, triglycerides, blood urea nitrogen, creatinine (and creatinine clearance by the Cockcroft-Gault formula), uric acid, bilirubin (total and direct), alkaline phosphatase, aspartate aminotransferase, alanine aminotransferase, γ glutamyltransferase, lactate dehydrogenase, creatine kinase, cardiovascular marker panel, and high-sensitivity C-reactive protein;
- Urinalysis: appearance, colour, pH, specific gravity, glucose, blood, bilirubin, leukocyte esterase, ketones, nitrates, urine protein, urine creatinine, protein/creatinine ratio. Microscopic urinalysis will be performed if urinalysis results are abnormal.

Pregnancy testing will be performed for all women of childbearing potential. Urine dipstick or serum pregnancy testing will be performed at Visit 0. Serum pregnancy testing will be performed for all other applicable visits.

Summary tables presenting observed values and changes from baseline over time will be presented for continuous laboratory parameters by treatment group. Categorical laboratory parameters will be summarised using the frequency counts and percentages.

All relevant laboratory parameters will be classified as Low, Normal, and High according to the normal ranges if applicable. Shift tables of baseline categories versus categories at each postbaseline scheduled visit and the worst postbaseline value will be provided. Worst postbaseline value is the smallest value for criteria below a certain threshold or the largest value for criteria above a certain threshold. If a patient has a value below the threshold and above the threshold, the value furthest from the threshold will be chosen.

All laboratory data with normality status will be presented in a listing.

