7.8.4 Safety Analyses

Safety analysis except by-visit summarisations will be presented in 2 ways, one based on only the assessments during the double blind treatment phase, and another based on the assessments during the whole study.

Adverse events will be summarised by presenting for both treatment groups the number and percentage of patients having any AE, having an AE in each MedDRA primary system organ class, and having each individual AE (preferred term). Additionally, a summary of AEs by preferred term and severity will be performed using the worst severity grade.

All related AEs, AEs with outcome death, AEs leading to permanent discontinuation of treatment, SAEs, and related SAEs will be summarised by percentages and frequencies and listed including the investigator term, the preferred term, start and end dates of the AE, duration (days), severity, drug relationship, action taken, and outcome.

Treatment-related AEs are those rated by the investigator as “definite,” “probable,” or “possible.” In case the relationship is unknown or missing, the worst case will be assumed and the AE will be considered to be drug related.

For laboratory data, the proportion of patients with clinically significant abnormal values as reported by the investigator will be provided by laboratory parameter, dose cohort, and scheduled visit.

For each laboratory parameter, shift tables of baseline categories based on normal ranges (below, within, above) versus categories at each postbaseline scheduled visit and the worst postbaseline value will be provided.

Summary statistics of values and changes from baseline over time will be computed for all safety laboratory parameters.

For vital sign measurements, supine or seated blood pressure and HR (absolute values and change from baseline) will be summarised by dose cohort and scheduled visit.

For ECGs, the proportion of patients with a clinically significant abnormal ECG result will be provided. A summary of shifts in 12-lead ECG abnormalities from baseline will be provided by scheduled visits.

Abnormal physical examination data will be summarised by treatment group and body system with number and percentage of patients.

Previous and concomitant treatments coded using the WHO Drug Dictionary and medical history coded using MedDRA will be summarised by treatment group number and percentage of patients at different coded terms.

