3.1. Overall Study Design and Plan

This is a randomised, double-blind, placebo-controlled, multicentre, multinational, prospective study in patients with operable CTEPH prior to PEA with high preoperative PVR (>800 $\text{dyn}\cdot\text{s}\cdot\text{cm}^{-5}$). Eligible patients will be randomly assigned to riociguat or matching placebo 3 times a day (tid) in a 1:1 ratio. A total of 88 patients are planned to randomly assign at 4 sites in North America and Europe.

A schematic of the study design is presented in Figure 3-1.

Figure 3-1 Study Schematic

Abbreviations: PEA, pulmonary endarterectomy; RHC, right heart catheterisation; V, visit

Patients will undergo a screening period of up to 89 days prior to baseline (Visit 1). Following completion of the pretreatment screening phase, eligible study patients will be randomly assigned into the study.

The study will comprise 3 study periods:

- **Screening Period (Day -89 to Day 1):** The screening period of up to 90 days will be used to assess eligibility of patients and to allow for the washout of prohibited medications. Screening visit (V0) and randomisation visit (V1) can occur on the same day.
- **Treatment Period (Day 1 [Baseline] through Day 90):** Patients will be randomly assigned on Day 1 to receive either riociguat or matching placebo tid in a 1:1 ratio for 3 months. The study drug will be initiated at 1 mg and the dosage can be increased by 0.5 mg at 2-week intervals based on tolerability (systolic blood pressure [SBP]) up to a maximum dose of 2.5 mg tid based on the algorithm mentioned in Section 3.4. The study drug will be initiated no later than 180 days after right heart catheterisation (RHC) (used for screening of patients) and within 90 days of planned RHC before PEA. At Visit 2, RHC will be performed per site procedures no more than 1 week prior to PEA, which will be conducted by the principal surgeon of the site. The study drug will be discontinued once PEA is performed. The last study dose will be given on the morning of PEA surgery. The patient will remain hospitalised per the investigator's discretion.
- **Follow-up Period:** A follow-up visit is planned at 6 months after PEA, at which time RHC will also be performed per study site procedures.

A telephonic call visit is planned during treatment period and at Day 186±10 during follow-up period, where treating physician or designee will call patient to ask questions related to patient's well-being and any adverse events.

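### The worst-postbaseline laboratory shift in SAP 9.2 pools on-drug and postoperative values, and the treatment-phase version that Protocol 7.8.4 calls for is neither planned nor declared as dropped

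*SAP*

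**What the plan says.** **Protocol 7.8.4** sets a general rule: "Safety analysis except by-visit summarisations will be presented in 2 ways, one based on only the assessments during the double blind treatment phase", with a second presentation covering the whole study. For laboratory parameters the same section asks for shift tables of baseline category against "categories at each postbaseline scheduled visit and the worst postbaseline value will be provided".

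**SAP 9.2** repeats the tables: "Shift tables of baseline categories versus categories at each postbaseline scheduled visit and the worst postbaseline value will be provided". It defines the worst value as follows: "Worst postbaseline value is the smallest value for criteria below a certain threshold or the largest value for criteria above a certain threshold". When a patient has values on both sides, it adds: "If a patient has a value below the threshold and above the threshold, the value furthest from the threshold will be chosen". None of these sentences names a study period.

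**SAP 9.2** also provides for unplanned sampling. If a laboratory parameter of interest shifts significantly from baseline, "patients will then be scheduled for an interim visit within 2 weeks to have the laboratory measurements repeated".

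**SAP 3.1** fixes the end of treatment: "The study drug will be discontinued once PEA is performed", with the last dose on the morning of surgery.

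**SAP Section 11** lists the changes from the protocol. Its only laboratory entry removes the table of investigator-reported clinically significant values.

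**The concern.** The worst-postbaseline row is the one laboratory shift summary that reaches across visits. As written, it draws on values taken on study drug and on values taken after a major operation, when study drug has stopped. If surgery moves a parameter out of range in many patients of both arms, the row will describe surgery as well as treatment. A difference between arms that arose on drug will then look smaller in that row.

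The protocol's two-way presentation would separate the two periods, and the SAP does not carry it into the laboratory section. The laboratory assessments are part of the safety endpoints (SAP 3.2.4), and safety and tolerability is a secondary objective (SAP 2.2). The gap therefore touches a stated aim, though only through one summary.

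**Working it through.** The plan gives no figure to reproduce here. The check is a comparison of texts, followed by an illustration on assumed rates.

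**1. Does the protocol's rule cover this row?** The rule exempts by-visit summaries. The shift at each scheduled visit is such a summary. The worst-value shift takes one value per patient across visits, so it is not, even if it is printed in the same table. The rule applies.

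**2. Which values can enter the row?** From the schedule of events (Protocol Table 12-1, SAP 13.1):

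| Postbaseline laboratory visit | Timing | Study drug |
|---|---|---|
| Visit 2 (pre-PEA) | Day 90+30 | on |
| Visit 3 (post-PEA) | Day 96 | off |
| Visit 4 (follow-up) | Day 276±10 | off |

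Two of the three scheduled postbaseline visits are off drug. With no period limit, either can supply the worst value.

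**3. Is a period split given elsewhere in the SAP?** Yes. Sections 9.1.1 to 9.1.6 add a V0 to V3 version of the adverse event tables, and 9.1.7 splits events of special interest into V0 to V2 and V0 to V4. Section 9.2 has no counterpart, and Section 11 does not mention one being dropped.

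**4. What does the Visit 2 shift table already cover?** It shows every scheduled on-drug laboratory shift by arm. It does not include unscheduled on-drug samples, because the by-visit tables are limited to scheduled visits. Such samples could appear only in the worst-value row. A repeat triggered at Visit 2 may itself fall after PEA: the Visit 2 catheterisation is at most 7 days before surgery, and the repeat window is 2 weeks (14 days).

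**5. How can a postoperative value displace an on-drug one?** Suppose a patient is below the normal range on drug and above it, by a larger margin, after surgery. The furthest-value rule keeps only the high value, and the on-drug low drops out of the row. If both values are abnormal in the same direction, the category stays the same, but the row cannot distinguish this patient from one who was abnormal only after surgery.

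**6. Illustration of the dilution.** The documents give no abnormality rates, so all rates here are assumptions. Let p be the on-drug rate of shift to abnormal in one direction. Let q be the rate of a same-direction abnormal postoperative value, equal in both arms and independent of p.

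Rate in the pooled row = 1 − (1 − p)(1 − q), so the difference between arms = (p₁ − p₂)(1 − q).

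With p₁ = 30% and p₂ = 10%:

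| q | Pooled row | Difference |
|---|---|---|
| 0 | 30% vs 10% | 20 points |
| 25% | 47.5% vs 32.5% | 15 points |
| 50% | 65% vs 55% | 10 points |
| 75% | 82.5% vs 77.5% | 5 points |
| 90% | 93% vs 91% | 2 points |

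For example, at q = 50%: 1 − 0.70 × 0.50 = 65% and 1 − 0.90 × 0.50 = 55%. The Visit 2 table is unaffected by q and keeps its full difference.

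**The case against.** The strongest reply is that little is lost. The sentence that defines the worst-value row also provides a shift table at each scheduled visit, and Visit 2 is the only scheduled postbaseline laboratory visit before PEA. SAP 9.2 further tabulates observed values and changes over time by arm and lists all laboratory data. Protocol 6.3.6 has clinically significant abnormalities recorded as adverse events, apart from those tied to the underlying disease and no more severe than expected. This stands. A reader might infer that on-drug abnormalities are hidden, but the documents do not support that.

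A reader might also infer that Visit 3 values will dominate the row. Neither document gives a postoperative abnormality rate, and the effect of surgery would vary across a panel that includes lipids, glycated haemoglobin and urinalysis. The supportable statement is that postoperative values can set the category.

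Third, unscheduled on-drug samples may be few. The first scheduled postbaseline sample is Visit 2, shortly before surgery, and the SAP does not say outright that unscheduled values count towards the worst value. For many patients a treatment-phase worst value may equal the Visit 2 value. This also stands, and it limits the size of the point.

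Finally, the SAP's silence might be taken to mean that the protocol's rule simply carries over. That is a weak defence: the SAP spells out period versions for adverse events and lists its departures, so a programmer following 9.2 would produce one table.

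**Conclusion.** The point holds as a minor one. SAP 9.2 plans a single worst-postbaseline laboratory shift with no period limit, Protocol 7.8.4 calls for a treatment-phase version as well, and Section 11 does not declare the departure. These three facts rest on the text alone.

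The loss is limited to one thing: a pooled on-drug summary that includes unscheduled on-drug values and is protected from displacement by postoperative ones. Its size cannot be computed from the documents. The factor of (1 − q) depends on assumed rates, on equal postoperative rates in both arms and on independence. It describes the pooled row only, not the laboratory evidence as a whole. A statement about statistical power would be out of place, since the plan tests no laboratory shifts.

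**What to change.** In SAP 9.2, produce the worst-postbaseline shift table twice:

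1. **Double-blind treatment phase**, with the window stated and unscheduled samples inside it included. A suggested window is first dose to PEA, or to last dose for patients who do not have PEA. The protocol gives no such cut-off for the analysis, so it needs to be written down. Taking the treatment period in SAP 3.1 literally (Day 1 through Day 90) would exclude a Visit 2 sample drawn later in its Day 90+30 window, which runs to Day 120.
2. **Whole study**, as now. Repeat samples drawn after PEA count only here.

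Apply the furthest-value rule within each window separately, and say explicitly that unscheduled samples enter the worst value. If the sponsor prefers a single table, Section 11 should at least declare and justify the departure, although that closes only the documentation gap.

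The cost is a few lines of SAP text and one more run of an existing table. No new data are needed.

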13.1. Schedule of Events

	Visit 0 Pretreatment / Screening	Visit 1 Randomisation & baseline visit	Visit 2 RHC visit (Pre- PEA)	Visit 3 Post-PEA	Visit 4 Follow-up visit incl. RHC
Time frame	Day -89 to 1	Day 1	Day 90+30	Day 96 ^a	Day 276±10
Activity / Observation					
Written informed consent	X				
Inclusion/exclusion criteria review	X	(X) ^b			
Assessment of current tobacco use	X				
Demographic data including height and weight	X				
HIV test	(X) ^b	X			
Medical and treatment history	X	X			
Physical examination including WHO functional class	X	X	X	X	X
Vital sign measurements	X	X	X	X	X
Clinical laboratory assessments (haematology, clinical chemistry, and urinalysis)	(X) ^b	X	X	X	X
NT-proBNP measurement		X	X		X
Haemodynamics incl. PVR, mRAP, mPAP, cardiac index, pulmonary artery wedge pressure measurement	X ^c		X		X
12-lead ECG		X	X		X
Pregnancy test (if applicable) ^d	X	X	X		X
Randomisation/treatment assignment		X			
Administration of double-blind study drugs ^e		X	X		
Provision of patient diary	X				

	Visit 0 Pretreatment / Screening	Visit 1 Randomisation & baseline visit	Visit 2 RHC visit (Pre- PEA)	Visit 3 Post-PEA	Visit 4 Follow-up visit incl. RHC
Time frame	Day -89 to 1	Day 1	Day 90+30	Day 96 ^a	Day 276±10
Activity / Observation					
Perioperative assessment (circulatory arrest time, surgery-related complications)			X ^f		
Surgical evaluation of specimen ^g				X ^g	
Hospital and ICU length of stay				X	
Time on mechanical ventilation				X	
PAH-targeted therapy assessment	X	X	X	X	X
PH-related hospitalisation		X	X	X	X
Adverse event monitoring	X	X	X	X	X
Concomitant medications		X	X	X	X
Return of patient diary				X	
Return of study drug				X	
Telephone call			X ^h		X ⁱ
Patient compliance check (study procedures and study drug)		X	X	X	X

Abbreviations: ECG, electrocardiogram; HIV, human immunodeficiency virus; ICU, intensive care unit; incl., including; mPAP, mean pulmonary arterial pressure; mRAP, mean right atrial pressure; NT-proBNP, N-terminal pro-B-type natriuretic peptide; PAH, pulmonary arterial hypertension; PEA, pulmonary endarterectomy; PH, pulmonary hypertension; PVR, pulmonary vascular resistance; RHC, right heart catheterisation; WHO, World Health Organization

^a The PEA will be conducted by the principal surgeon of the site within a week of RHC.

^b When laboratory analysis results are required/available (see Protocol Section 4.2)

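### The worst-postbaseline laboratory shift in SAP 9.2 keeps one direction per patient by an undefined distance, so that row understates two-directional abnormalities

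*SAP*

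**What the plan says.** SAP 9.2 first sets the categories: "All relevant laboratory parameters will be classified as Low, Normal, and High according to the normal ranges if applicable". It then sets the scope of the tables: "Shift tables of baseline categories versus categories at each postbaseline scheduled visit and the worst postbaseline value will be provided". The worst value is defined by direction: "Worst postbaseline value is the smallest value for criteria below a certain threshold or the largest value for criteria above a certain threshold". A tie-break follows for patients who have both: "If a patient has a value below the threshold and above the threshold, the value furthest from the threshold will be chosen".

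Protocol 7.8.4 plans the same two parts (baseline category "versus categories at each postbaseline scheduled visit and the worst postbaseline value will be provided") but has no tie-break. It also says that safety analyses other than by-visit summaries are to be shown twice, once for the double-blind treatment phase and once for the whole study. SAP 9.2 does not repeat that split, and SAP section 11 does not list it among the changes from the protocol.

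Three other places bear on the point:

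- SAP 9.2 provides for repeat tests outside the schedule: after a significant shift, "patients will then be scheduled for an interim visit within 2 weeks to have the laboratory measurements repeated".
- SAP 9.2 also keeps a full record: "All laboratory data with normality status will be presented in a listing".
- SAP section 11, item 3, removes the protocol's table of laboratory values that investigators judged clinically significant, because the data will not be available.

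**The concern.** The definition of the worst value is sound in each direction taken alone: a minimum for low criteria and a maximum for high criteria. The tie-break merges the two into one category per patient and parameter. Two things follow.

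- In the worst-value row, a patient who has been both below and above the normal range always loses one direction. That row is the only part of the shift table that counts each patient once over the postbaseline period. It therefore cannot show how many patients were ever low, or how many were ever high.
- The choice of direction cannot be reproduced from the text. The sentence refers to one threshold where there are two limits. It does not say whether distance is absolute or relative to the limit. Two programmers could follow it faithfully and put the same patient in opposite categories.

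What is at stake is the accuracy of one safety display. It matters somewhat more because, with the clinically-significant table gone, the shift tables become the main tabulation of laboratory abnormalities by arm.

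**Working it through.** The documents state no figure on this point, so there is none to reproduce. The check applies the rule to examples. Limits and values are assumed for illustration and are not trial data.

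**Inputs from the documents**

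- Scheduled postbaseline samples: Visits 2, 3 and 4. Visit 1 is baseline (SAP 13.1, row "Clinical laboratory assessments (haematology, clinical chemistry, and urinalysis").
- Planned number randomised: 88 (SAP 4.1).

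**Two readings of distance**

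- Absolute: lower limit minus value, or value minus upper limit.
- Relative: the same difference divided by the limit that was crossed.

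**Example A**, assumed range 3.5 to 5.1, values 2.8 and 6.0

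- Absolute: 3.5 − 2.8 = 0.7 below; 6.0 − 5.1 = 0.9 above. The row shows High.
- Relative: 0.7 / 3.5 = 20.0% below; 0.9 / 5.1 = 17.6% above. The row shows Low.

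**Example B**, assumed range 150 to 400, values 60, 520 and 250 at Visits 2, 3 and 4

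- Absolute: 150 − 60 = 90 below; 520 − 400 = 120 above. The row shows High.
- Relative: 90 / 150 = 60% below; 120 / 400 = 30% above. The row shows Low.

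In both examples the scale alone reverses the category.

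**What each display shows for Example B**

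| Display | Result |
|---|---|
| By-visit shift rows, current SAP | Low, High, Normal |
| Worst-value row, absolute distance | High only |
| Worst-value row, relative distance | Low only |
| Separate rows for minimum and maximum | Low and High |

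**Where the loss is complete.** A value from Visit 2, 3 or 4 that the tie-break drops still appears in its own by-visit row. A value from an interim visit has no by-visit row. It is missing from every shift table only if the worst value draws on unscheduled samples and the tie-break then discards it. SAP 9.2 does not say whether unscheduled samples count.

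**How many patients.** No rate of two-directional abnormality is given. Over an assumed 1% to 10% per parameter:

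- 88 × 0.01 = 0.88, or about 0.9 patients
- 88 × 0.10 = 8.8 patients

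With 44 per arm, the figures are 0.44 and 4.4.

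**The case against.** The strongest reply is that little information disappears.

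- By-visit rows at Visits 2, 3 and 4 keep both directions when they occur at scheduled visits, and every value is listed.
- Observed values are summarised with minimum and maximum, so extremes in both directions are visible.
- Under protocol 6.3.6, abnormal results judged clinically significant are to be recorded as adverse events, with an exception for findings tied to the underlying disease.
- Choosing one mutually exclusive worst category could be called a display preference.

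Most of this stands, and it limits the size of the point. Two things survive it. By-visit counts cannot be added up to patients ever low or ever high, because one patient may appear at several visits, and a listing gives no counts by arm. And no other display cures a rule whose result depends on an unstated scale.

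A reader might also infer more than the documents support:

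- *That one abnormality vanishes from the laboratory shift tables altogether.* The same section requires the by-visit rows, so this does not follow for scheduled samples.
- *That a postoperative extreme at Visit 3 will hide an opposite on-treatment abnormality.* In a whole-study worst-value row it can. But protocol 7.8.4 calls for a double-blind-phase version as well, and post-PEA values would not enter that. If only scheduled samples count, Visit 2 is the sole postbaseline sample in that phase and the tie-break has nothing to act on. The SAP's silence leaves the split unconfirmed; it does not withdraw it.
- *That the worst-value row is known to cover unscheduled samples.* The SAP mentions unscheduled assessments when it defines baseline (section 4), not here.
- *That patients with abnormalities go uncounted.* The patient is still counted as abnormal in the row; only the second direction is missing.

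**Conclusion.** The point holds for the worst-postbaseline row of the laboratory shift table. That row gives one category to a patient with values outside both limits, so it understates two-directional abnormalities. The category rests on a distance whose reference limit and scale are undefined, and in both worked examples the scale reverses the result.

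The point is minor. The number of patients affected is unknown; 0.9 to 8.8 of 88 per parameter rests wholly on the assumed rates of 1% to 10%. Nothing in the documents suggests that such patients are common or differ in number between arms. Complete loss across the shift tables requires the dropped value to be unscheduled and the worst value to use unscheduled samples, and the second condition is an assumption. No efficacy endpoint is touched. The change is still worth making because it costs almost nothing and replaces a rule that cannot be programmed unambiguously.

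**What to change.** In SAP 9.2:

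1. Delete the tie-break sentence. The direction-specific definition before it can stay.
2. Replace the single worst-value shift with two: baseline category against the category of the postbaseline minimum (worst-low), and baseline category against the category of the postbaseline maximum (worst-high). Count a patient in both when both occur.
3. Present both for the double-blind phase and for the whole study, as protocol 7.8.4 already requires.
4. State whether unscheduled and interim samples feed the minimum and maximum.

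The cost is a short SAP edit and a slightly larger table, with no new data. The low and high counts will no longer be mutually exclusive, which a footnote can explain.
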